### 5.1.3 Subject Exclusion Criteria

The subject must be excluded from participating in the trial if the subject:

#### Cohort #1

1. Is currently participating and receiving study therapy or has participated in a study of an investigational agent and received study therapy or used an investigational device within 4 weeks of the first dose of treatment.

NOTE: Subjects who were treated on a clinical study of allogeneic stem cell transplant (alloHSCT) will be eligible if they are at least 3 months after allogeneic HCT and are at least 3 weeks ( $>21$  days) off of all immune suppression and have no evidence of active GVHD (physiologic corticosteroid replacement therapy for adrenal or pituitary insufficiency is allowed). **Subjects with prior alloHSCT will not be eligible for enrollment during the safety run in phase.**

2. Has a diagnosis of immunodeficiency or is receiving systemic steroid therapy or any other form of immunosuppressive therapy within 7 days prior to the first dose of trial treatment.
3. Has a known history of active TB (Bacillus Tuberculosis)
4. Hypersensitivity to pembrolizumab or any of its excipients.
5. Has had a prior anti-cancer monoclonal antibody (mAb) within 4 weeks prior to study Day 1 or who has not recovered (i.e.,  $\leq$  Grade 1 or at baseline) from adverse events due to agents administered more than 4 weeks earlier.
6. Has had prior chemotherapy, targeted small molecule therapy, or radiation therapy within 2 weeks or growth factors within 1 week prior to study Day 1 or who has not

recovered (i.e.,  $\leq$  Grade 1 or at baseline) from adverse events due to a previously administered agent.

- Note: Subjects with  $\leq$  Grade 2 neuropathy are an exception to this criterion and may qualify for the study.
- Note: If subject received major surgery, they must have recovered adequately from the toxicity and/or complications from the intervention prior to starting therapy.

7. Has a known additional malignancy that is progressing or requires active treatment. Exceptions include basal cell carcinoma of the skin or squamous cell carcinoma of the skin that has undergone potentially curative therapy or in situ cervical cancer.
8. Has known active central nervous system (CNS) leukemia. Subjects with previously treated CNS leukemia may participate provided that they have documented clearance of CNS leukemia and are not actively treated with intrathecal chemotherapy.
9. Has active autoimmune disease that has required systemic treatment in the past 2 years (i.e. with use of disease modifying agents, corticosteroids or immunosuppressive drugs). Replacement therapy (eg., thyroxine, insulin, or physiologic corticosteroid replacement therapy for adrenal or pituitary insufficiency, etc.) is not considered a form of systemic treatment. Subjects that require intermittent use of bronchodilators or local steroid injections will not be excluded from the study.
10. Has known history of non-infectious pneumonitis that required steroids or current pneumonitis.
11. Has an active uncontrolled infection requiring systemic therapy (viral, bacterial or fungal). Patients with infection under active treatment and controlled with antibiotics are eligible.
12. Has a white blood cell count  $> 30 \times 10^9/L$ .

NOTE: Leukapheresis and Hydroxyurea is permitted to meet this criterion and should be stopped  $\geq 12$  hours before starting treatment on the study.

13. Has a history or current evidence of any condition, therapy, or laboratory abnormality that might confound the results of the trial, interfere with the subject's participation for the full duration of the trial, or is not in the best interest of the subject to participate, in the opinion of the treating investigator.
14. Has known psychiatric or substance abuse disorders that would interfere with cooperation with the requirements of the trial.

15. Is pregnant or breastfeeding, or expecting to conceive or father children within the projected duration of the trial, starting with the pre-screening or screening visit through 120 days after the last dose of trial treatment.
16. Has received prior therapy with an anti-PD-1, anti-PD-L1, or anti-PD-L2 agent.
17. Has a known history of Human Immunodeficiency Virus (HIV) (HIV 1/2 antibodies).
18. Has known active Hepatitis B (e.g., HBsAg reactive) or Hepatitis C (e.g., HCV RNA [qualitative] is detected).
19. Has received a live vaccine within 30 days of planned start of study therapy.

*Note: Seasonal influenza vaccines for injection are generally inactivated flu vaccines and are allowed; however intranasal influenza vaccines (e.g., Flu-Mist®) are live attenuated vaccines, and are not allowed.*

### **Cohort #2**

1. Is currently participating and receiving study therapy or has participated in a study of an investigational agent and received study therapy or used an investigational device within 4 weeks of the first dose of treatment for pre-existent myeloid disorder such as MDS or MPN.
2. Is eligible for treatment with a standard cytarabine and anthracycline or similar intensive induction chemotherapy, or is willing to receive intensive induction therapy. If subject is not considered eligible for treatment with standard or similar intensive induction chemotherapy due to comorbidities or other factors, or is unwilling to receive intensive induction therapy will be allowed to participate in this study.
3. Has a diagnosis of immunodeficiency or is receiving systemic steroid therapy or any other form of immunosuppressive therapy within 7 days prior to the first dose of trial treatment.
4. Has a known history of active TB (Bacillus Tuberculosis)
5. Hypersensitivity to pembrolizumab or any of its excipients.
6. Has had a prior anti-cancer monoclonal antibody (mAb) within 4 weeks prior to study Day 1 or who has not recovered (i.e.,  $\leq$  Grade 1 or at baseline) from adverse events due to agents administered more than 4 weeks earlier.
7. Has had prior chemotherapy, targeted small molecule therapy, or radiation therapy within 2 weeks or growth factors within 1 week prior to study Day 1 or who has not

recovered (i.e.,  $\leq$  Grade 1 or at baseline) from adverse events due to a previously administered agent.

- Note: Subjects with  $\leq$  Grade 2 neuropathy are an exception to this criterion and may qualify for the study.
- Note: If subject received major surgery, they must have recovered adequately from the toxicity and/or complications from the intervention prior to starting therapy.

8. Has a known additional malignancy that is progressing or requires active treatment. Exceptions include basal cell carcinoma of the skin or squamous cell carcinoma of the skin that has undergone potentially curative therapy or in situ cervical cancer.
9. Has known active central nervous system (CNS) leukemia. Subjects with previously treated CNS leukemia may participate provided that they have documented clearance of CNS leukemia and are not actively treated with intrathecal chemotherapy.
10. Has active autoimmune disease that has required systemic treatment in the past 2 years (i.e. with use of disease modifying agents, corticosteroids or immunosuppressive drugs). Replacement therapy (eg., thyroxine, insulin, or physiologic corticosteroid replacement therapy for adrenal or pituitary insufficiency, etc.) is not considered a form of systemic treatment. Subjects that require intermittent use of bronchodilators or local steroid injections will not be excluded from the study.
11. Has known history of non-infectious pneumonitis that required steroids or current pneumonitis .
12. Has an active uncontrolled infection requiring systemic therapy (viral, bacterial or fungal). Patients with infection under active treatment and controlled with antibiotics are eligible.
13. Has a white blood cell count  $> 30 \times 10^9/L$ .

NOTE: Leukapheresis and hydroxyurea is permitted to meet this criterion and should be stopped  $\geq 12$  hours before starting treatment on the study.

14. Has a history or current evidence of any condition, therapy, or laboratory abnormality that might confound the results of the trial, interfere with the subject's participation for the full duration of the trial, or is not in the best interest of the subject to participate, in the opinion of the treating investigator.
15. Has known psychiatric or substance abuse disorders that would interfere with cooperation with the requirements of the trial.

16. Is pregnant or breastfeeding, or expecting to conceive or father children within the projected duration of the trial, starting with the pre-screening or screening visit through 120 days after the last dose of trial treatment.
17. Has received prior therapy with an anti-PD-1, anti-PD-L1, or anti-PD-L2 agent.
18. Has a known history of Human Immunodeficiency Virus (HIV) (HIV 1/2 antibodies).
19. Has known active Hepatitis B (e.g., HBsAg reactive) or Hepatitis C (e.g., HCV RNA [qualitative] is detected).
20. Has received a live vaccine within 30 days of planned start of study therapy.

*Note: Seasonal influenza vaccines for injection are generally inactivated flu vaccines and are allowed; however intranasal influenza vaccines (e.g., Flu-Mist®) are live attenuated vaccines, and are not allowed.*

## 5.2 Trial Treatments

The treatment to be used in this trial is outlined below in Table 1

Table 1. Trial Treatment

Drug	Dose/ Potency	Dose Frequency	Route of Administration	Regimen/Treatment Period	Use
Azacitidine	75 mg/m 	Daily x 7 days	Subcutaneous (SQ) or IV infusion	Day 1 to 7 of each 28 day cycle	Standard
Pembrolizumab	200 mg	Q 3W	IV infusion	*# Starting on Day 8 of Cycle 1	Experimental

- \*Pembrolizumab administration will start on Day 8 of Cycle 1.
- # On days when both agents are administered, azacitidine should be administered before the pembrolizumab. An anti-emetic, preferably a serotonin antagonist, should be administered prior to azacitidine; the individual anti-emetic selected is at the discretion of the investigator.

Trial treatment should begin as close as possible to the date on which treatment is allocated/assigned.

## 5.2.1 Dose Selection/Modification

### 5.2.1.1 Dose Selection

The rationale for selection of doses to be used in this trial is provided in Section 4.0 – Background and Rationale.

Details on preparation and administration of pembrolizumab (MK-3475) are provided in the Pharmacy Manual.

Azacitidine will be administered at the dose and schedule approved by the FDA for treatment of MDS/AML. The azacitidine IV/SQ will be administered before the dose of pembrolizumab on days that both agents are administered.

### 5.2.1.2 Dose Modification (Escalation/Titration/Other)

- Dose modifications will be made based on Common Terminology Criteria for Adverse Events (CTCAE) grading (version 4.0)
- Patients may remain on study and therapy even if one of the agents are discontinued due to toxicity. No more than two dose reductions of any agent is allowed.

### 5.2.1.3 Dose Limiting Criteria

- Dose limiting toxicities during **safety run in phase** will be determined during Cycle 1, Cycle 2, and Cycle 3 of study treatment. Adverse events that occur after the first three cycles will also be evaluated by investigator and may be considered as dose limiting.
- Subjects with AML have frequently  $\geq$  grade 3 cytopenias; thus, will be un-evaluable for hematologic DLT with the exception listed below.
- For hematologic toxicity, the only adverse event that will be considered dose limiting is:
  - grade  $\geq$  4 neutropenia and thrombocytopenia with a hypocellular bone marrow and no evidence of residual leukemia lasting for 42 days

NOTE: only patients evaluable for hematologic toxicity as defined in Section 5.2.1.5.2.1, 5.2.1.5.2.3 and Section 5.2.1.5.3 may need to have a bone marrow assessment after cycle 1 if no count recovery to baseline. Otherwise, all patients will have bone marrow after cycle 2);

- For non-hematologic toxicities, the only adverse events that will be considered dose-limiting are:

- Any grade 4 toxicity considered at least possibly related to study drugs excluding asymptomatic electrolyte aberrations that can be corrected to  $\leq$  grade 2 and excluding specific toxicities that are frequent in AML population such as fever, infections, fatigue, bleeding, bone pain.
- Any grade 3 toxicity considered at least possibly related to study drugs that does not resolve to  $\leq$  grade 2 within 48 hours with the exception of Grade 3 anorexia, nausea, vomiting, diarrhea, or mucositis if it resolves to  $\leq$  grade 2 within 72 hours of maximal supportive care; asymptomatic electrolyte abnormalities that can be corrected to  $\leq$  grade 2 and excluding specific toxicities that are frequent in AML population such as fever, infections, fatigue, bleeding, bone pain. Grade 3 neurotoxicity and nephrotoxicity of any duration will be considered dose-limiting if at least possibly drug-related.

Table 3. Safety Run In Phase- Dose De-escalation Rules

Number of patients with DLT during run in phase (Planned 6 patients)	Decision rule
0 or 1 out of 3 in Cycle 1	Enter 3 more patients
$\geq$ 2 of 3 in Cycle 1 OR $\geq$ 2 of 6 in Cycle 1	Patients will be assessed for safety. Based on the complete assessment of AEs, the dose reduction as proposed in the Section 2.1 and 2.2.
$\geq$ 2 of 6 in Cycle 2 or/and Cycle 3 OR $\geq$ 2 of 6 in Cycle 1+2+3	Patients will be assessed for safety. Based on the complete assessment of AEs, the dose reduction as proposed in the Section 2.1 and 2.2.
$\leq$ 1 of 6 in Cycle 1 + 2 + 3	Open Phase II Cohort 1 and Cohort 2.

#### 5.2.1.4 Immune Adverse Events Associated with Pembrolizumab

Adverse events (both non-serious and serious) associated with pembrolizumab exposure may represent an immunologic etiology. These adverse events may occur shortly after the first dose or several months after the last dose of treatment. Pembrolizumab must be withheld for drug-related toxicities and severe or life-threatening AEs as per Table 4 below. See Section 5.7.5 for supportive care guidelines, including use of corticosteroids.

Table 4. Dose Modification and Toxicity Management Guidelines for Immune-related AEs Associated with Pembrolizumab

General instructions:
1. Corticosteroid taper should be initiated upon AE improving to Grade 1 or less and continue to taper over at least 4 weeks.

2. For situations where pembrolizumab has been withheld, pembrolizumab can be resumed after AE has been reduced to Grade 1 or 0 and corticosteroid has been tapered. For Grade 3 (excluding alopecia, fatigue) toxicities which are eligible for re-dosing: Increase dose interval to every 4 weeks, and to every 6 weeks with second occurrence. Pembrolizumab should be permanently discontinued if AE does not resolve within 12 weeks of last dose or corticosteroids cannot be reduced to  $\leq 10$  mg prednisone or equivalent per day within 12 weeks.
3. For severe and life-threatening irAEs, IV corticosteroid should be initiated first followed by oral steroid. Other immunosuppressive treatment should be initiated if irAEs cannot be controlled by corticosteroids.

Immune-related AEs	Toxicity grade or conditions (CTCAEv4.0)	Action taken to pembrolizumab	irAE management with corticosteroid and/or other therapies	Monitor and follow-up
Pneumonitis	Grade 2	Withhold	
 
• Administer corticosteroids (initial dose of 1-2 mg/kg prednisone or equivalent) followed by taper
 
	
 
• Monitor participants for signs and symptoms of pneumonitis
 
• Evaluate participants with suspected pneumonitis with radiographic imaging and initiate corticosteroid treatment
 
• Add prophylactic antibiotics for opportunistic infections
 

	Grade 3 or 4, or recurrent Grade 2	Permanently discontinue		
Diarrhea / Colitis	Grade 2 or 3	Withhold	
 
• Administer corticosteroids (initial dose of 1-2 mg/kg prednisone or equivalent) followed by taper
 
	
 
• Monitor participants for signs and symptoms of enterocolitis (ie, diarrhea, abdominal pain, blood or mucus in stool with or without fever) and of bowel perforation (ie, peritoneal signs and ileus).
 
• Participants with <math>\geq</math> Grade 2 diarrhea suspecting colitis should consider GI consultation and performing endoscopy to rule out colitis.
 

	Grade 4	Permanently discontinue		

				
 
Participants with diarrhea/colitis should be advised to drink liberal quantities of clear fluids. If sufficient oral fluid intake is not feasible, fluid and electrolytes should be substituted via IV infusion.
 

AST / ALT elevation or Increased bilirubin	Grade 2	Withhold	
 
Administer corticosteroids (initial dose of 0.5- 1 mg/kg prednisone or equivalent) followed by taper
 
	
 
Monitor with liver function tests (consider weekly or more frequently until liver enzyme value returned to baseline or is stable)
 

	Grade 3 or 4	Permanently discontinue	
 
Administer corticosteroids (initial dose of 1-2 mg/kg prednisone or equivalent) followed by taper
 
	
Type 1 diabetes mellitus (T1DM) or Hyperglycemia	Newly onset T1DM or Grade 3 or 4 hyperglycemia associated with evidence of $\beta$ -cell failure	Withhold	
 
Initiate insulin replacement therapy for participants with T1DM
 
Administer anti-hyperglycemic in participants with hyperglycemia
 
	
 
Monitor participants for hyperglycemia or other signs and symptoms of diabetes.
 

Hypophysitis	Grade 2	Withhold	
 
Administer corticosteroids and initiate hormonal replacements as clinically indicated.
 
	
 
Monitor for signs and symptoms of hypophysitis (including hypopituitarism and adrenal insufficiency)
 

	Grade 3 or 4	Withhold or permanently discontinue 		
Hyperthyroidism	Grade 2	Continue	
 
Treat with non-selective beta-blockers (eg, propranolol) or thionamides as appropriate
 
	
 
Monitor for signs and symptoms of thyroid disorders.
 

	Grade 3 or 4	Withhold or permanently discontinue 		
Hypothyroidism	Grade 2-4	Continue	
 
Initiate thyroid replacement hormones (eg, levothyroxine or liothyroinine) per standard of care
 
	
 
Monitor for signs and symptoms of thyroid disorders.
 

Nephritis and Renal dysfunction	Grade 2	Withhold	
 
Administer corticosteroids (prednisone 1-2 mg/kg or equivalent) followed by taper.
 
	
 
Monitor changes of renal function
 

	Grade 3 or 4	Permanently discontinue		

Myocarditis	Grade 1 or 2	Withhold	
 
Based on severity of AE administer corticosteroids
 
	
 
Ensure adequate evaluation to confirm etiology and/or exclude other causes
 

	Grade 3 or 4	Permanently discontinue		
All other immune-related AEs	Intolerable/persistent Grade 2	Withhold	
 
Based on type and severity of AE administer corticosteroids
 
	
 
Ensure adequate evaluation to confirm etiology and/or exclude other causes
 

	Grade 3	Withhold or discontinue based on the type of event. Events that require discontinuation include and not limited to: Gullain-Barre Syndrome, encephalitis		
	Grade 4 or recurrent Grade 3	Permanently discontinue		

1. Withhold or permanently discontinue pembrolizumab is at the discretion of the investigator or treating physician.
 
NOTE:
 
For participants with Grade 3 or 4 immune-related endocrinopathy where withhold of pembrolizumab is required, pembrolizumab may be resumed when AE resolves to <math>\leq</math> Grade 2 and is controlled with hormonal replacement therapy or achieved metabolic control (in case of T1DM).
				

Dosing interruptions are permitted in the case of medical / surgical events or logistical reasons not related to study therapy (e.g., elective surgery, unrelated medical events, patient vacation, and/or holidays). Subjects should be placed back on study therapy within 4 weeks of the scheduled interruption, unless otherwise discussed with the Sponsor. The reason for interruption should be documented in the patient's study record.

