Azacitidine administration should not be interrupted if pembrolizumab dosing is interrupted for toxicity except as defined above or at the discretion of the investigator for any clinical toxicities where ongoing administration of azacitidine is felt to be unsafe (grade 3 or 4 pembrolizumab-related toxicities). The azacitidine doses can be resumed in the same cycle if no more than a 5 day gap occurred, the patient is still likely to have clinical benefit, and the investigator feels that it is safe to restart azacitidine therapy. No dose reduction of azacitidine will be required.

Patients experiencing Grade 3 or 4 toxicities potentially attributable to pembrolizumab should have their pembrolizumab treatment interrupted regardless of when it occurs in the cycle until the toxicity resolves or returns to baseline.

Cycle duration maybe extended beyond 28 days to allow resolution of toxicities related to study treatments (see Table 4). In general, the next cycle of treatment should be restarted when drug-related toxicities resolve to  $\leq 1$ ; even if pembrolizumab cannot be administered (ongoing steroid taper), azacitidine should be restarted. The pembrolizumab can be restarted on any day

of the cycle when the criteria are met for its administration (steroids tapered to the required level) and according to the dose reduction recommendations.

If for unforeseen circumstances (for reasons other than toxicity, eg, emergency surgery, unrelated medical events, or logistical reasons not related to study therapy such as patient vacation, and/or holidays) the patient misses a doses of azacitidine within a cycle, the doses can be resumed in the same cycle if no more than a 5 day gap occurred and the patient is still likely to have clinical benefit. The dose of pembrolizumab within 7 days of surgery will be omitted.

If a treatment delay continues beyond Day 28 of the current cycle, then the day when azacitidine treatment is restarted will be counted as Day 1 of the next cycle.

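### Table 4 withholds pembrolizumab for Grade 1 myocarditis, yet its general restart rule lets a Grade 2 myocarditis resume once it has fallen to Grade 1

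*Combined protocol and SAP*

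**What the plan says.** Section 5.2.1.4 introduces Table 4 as binding: "Pembrolizumab must be withheld for drug-related toxicities and severe or life-threatening AEs as per Table 4 below". In the myocarditis row, Grades 1 and 2 carry the action withhold, and Grades 3 and 4 carry permanent discontinuation. The steroid column of that row reads "Based on severity of AE administer corticosteroids", with no dose and no grade at which steroids become obligatory.

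Three general instructions stand above the rows. Instruction 1 deals with the taper: "Corticosteroid taper should be initiated upon AE improving to Grade 1 or less and continue to taper over at least 4 weeks". Instruction 2 deals with restart after any hold: "pembrolizumab can be resumed after AE has been reduced to Grade 1 or 0 and corticosteroid has been tapered". It then lengthens the dosing interval for Grade 3 events ("toxicities which are eligible for re-dosing: Increase dose interval to every 4 weeks, and to every 6 weeks with second occurrence") and sets a 12-week limit, after which an unresolved event ends pembrolizumab. The only event-specific change to the release grade in Table 4 is the closing note on Grade 3 or 4 endocrinopathy.

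**The concern.** A hold rule and a release rule should divide the grades between them. If the hold covers Grades 1 and 2, release should need something better than Grade 1. Here the general release threshold suits events whose hold starts at Grade 2 or above. It was not adapted to the one event that the table holds from Grade 1.

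At stake is whether a patient with residual Grade 1 immune myocarditis is given more pembrolizumab. A site that follows instruction 2 may dose, and a site that follows the row would keep withholding. Both could point to Table 4 in support.

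**Working it through.** No sample size, error rate or event count is involved. The check sets the hold grades beside the release grades and then looks for any text that separates them.

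**Step 1. Lowest graded hold in each row of Table 4, against the release range of Grade 0 to 1.**

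| Row | Lowest graded hold | Overlaps 0–1? |
|---|---|---|
| Pneumonitis | 2 | No |
| Diarrhea/colitis | 2 | No |
| AST/ALT or bilirubin | 2 | No |
| Type 1 diabetes/hyperglycemia | 3 (new-onset diabetes is held without a grade) | No |
| Hypophysitis | 2 | No |
| Hyperthyroidism | 3 | No |
| Nephritis/renal dysfunction | 2 | No |
| Myocarditis | 1 | Yes |
| All other immune-related events | 2 | No |

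Hypothyroidism is left out because its only action is to continue. That leaves nine withholding rows, of which one overlaps.

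**Step 2. The overlap for myocarditis.** Hold grades are {1, 2} and release grades are {0, 1}. The common element is {1}. Grades 3 and 4 end treatment, so among the grades from which a restart is possible, {0, 1, 2}, the only one that the row does not withhold is {0}.

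**Step 3. Does the steroid condition separate the two states?** It delays re-dosing but does not change the grade. Under instruction 1 the taper begins at Grade 1 or less and lasts at least 4 weeks, which is 28 days. With doses every 21 days, 28/21 = 1.33, so one or two scheduled doses fall in that window if the taper must be finished first. The event may be Grade 1 throughout, and instruction 2 is still satisfied at the end.

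**Step 4. Does the longer dosing interval help?** No. It applies to Grade 3 events, and Grade 3 myocarditis is not re-dosed at all.

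**Step 5. Is there a myocarditis release grade elsewhere?** The supportive-care list in Section 5.7.5 has no myocarditis entry. The Table 4 closing note covers endocrinopathy only. The 12-week limit caps the hold but does not define the grade at which it ends. The causality table in Section 7.2.4 requires advance sponsor approval for some rechallenges but names no grade.

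**The case against.** The strongest reply is that hold and release describe different clinical situations. The row addresses an event that needs action: stop the drug, look for the cause, give steroids as severity demands. Instruction 2 addresses an event already treated and improving. Its language is permissive, whereas the hold is mandatory. On this reading a treated, residual Grade 1 is not the Grade 1 that the row has in mind. The reading is coherent, but Table 4 draws no such distinction, and for the other eight rows none is needed.

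Second, the rechallenge clause in Section 7.2.4 requires sponsor approval in advance when the earlier event was serious and possibly caused by pembrolizumab, or when re-exposure carries significant added risk. Re-dosing with residual myocarditis plausibly qualifies. This stands as a safeguard and makes unreviewed re-dosing less likely. It supplies no threshold, however, and refers the sponsor back to the protocol's dose-modification guidelines, where the gap lies.

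Third, the ordinary sense of a grade being reduced is a fall, so an event that starts at Grade 1 would have to reach Grade 0. That is the better reading. It leaves the milder onset with the stricter release condition, since a Grade 2 onset may still resume at Grade 1.

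A reader might infer more than the documents support:

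- **That Section 5.2.1.5.1 repeats the permissive rule.** Its sentence beginning "In general, the next cycle of treatment should be restarted when drug-related toxicities resolve to" governs when the next cycle, and so azacitidine, restarts. The text that follows restarts azacitidine even when pembrolizumab cannot be given, and leaves pembrolizumab to its own criteria.
- **That a Grade 1 onset managed without steroids has no minimum hold.** This needs an event that never changed grade to count as reduced, which would empty the Grade 1 hold of effect.
- **That the endocrinopathy note creates the same fault for hypophysitis.** A conflict with the Grade 3 or 4 rule in Section 5.2.1.5.1 depends on giving the word resolves a fixed grade there, which the protocol does not do. Extending the note to Grade 2 hypophysitis would loosen a restart rule without support in the documents.

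**Conclusion.** The point holds as a minor inconsistency in one row. As written, Table 4 permits pembrolizumab to resume at residual Grade 1 after a Grade 2 myocarditis, although the same table requires a hold at Grade 1. One of nine withholding rows is affected.

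The conclusion rests on two readings: that instruction 2 applies to every withheld event, as its wording says, and that the myocarditis row means Grade 1 however the patient arrived there. The row count compares graded holds only and sets aside the ungraded trigger for new-onset diabetes.

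The documents give no rate of Grade 1 or 2 myocarditis, so no frequency of re-dosing can be stated, and nothing in them shows that it occurred. The response endpoint, futility and toxicity boundaries and sample sizes are untouched.

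**What to change.** Add one sentence to general instruction 2 of Table 4: *For myocarditis, pembrolizumab may resume only at Grade 0 with any corticosteroid tapered.* Grade 0 follows from the table itself, as the only grade that the row does not withhold. It is still a clinical choice. Amendment 5 revised this table on the manufacturer's recommendations, so the wording should be confirmed with the manufacturer before it goes to sites. Section 5.2.1.5.1 should stay as it is, because an exception placed there could be taken to delay azacitidine.

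The cost is a short clarification and a longer pembrolizumab hold in what are presumably few cases. A case that lingers at Grade 1 could run into the 12-week limit and lose pembrolizumab. Azacitidine need not stop, since Section 5.2.1.2 lets a patient remain on therapy when one agent is discontinued.

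The reach is limited. Section 5.1.1 records Cohort 1 as complete and Cohort 2 as closed to accrual on 1/8/2020. Initial treatment may last 24 months from first dose, so a patient who started around that date could be treated until about January 2022, roughly 15 months after Amendment 8 of October 2020. Retreatment can add up to one year if the study remains open.
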